4.0 Protocol Design

This Phase 2 randomized, placebo-controlled, triple-blind, crossover, multi-site study will assess the safety and efficacy of four types of smoked marijuana to manage chronic, treatment-resistant PTSD symptoms among 76 veterans in an outpatient setting. The study will consist of a baseline period and three distinct study stages, which are described in detail below.

An initial 2-week screening period will be conducted to determine study eligibility prior to randomization, to obtain baseline measures of PTSD and substance use, to conduct study training, and ensure participants are willing and able to attend scheduled appointments and complete the study procedures.

Following randomization, participants will complete Stage 1, a three-week period of *ad-libitum* marijuana self-administration followed by a two-week period of marijuana abstinence (Cessation 1). This will be immediately followed by Stage 2, another three-week period of marijuana self-administration and two-week period of abstinence (Cessation 2). Stage 1 and Stage 2 will consist of identical procedures and measures, but the marijuana available to individual participants will vary.

During Stage 1, participants will be randomized to receive High THC, High CBD, THC/CBD, or Placebo marijuana to self-administer (up to 1.8 g/day) for the 3-week marijuana use period. As described in Section 4.2, randomization will be balanced across drug conditions (N=19 per marijuana type; total N=76). During Stage 2, the Placebo marijuana condition will be removed and all participants will be re-randomized to receive a different type of marijuana than they were assigned in Stage 1. Thus, Stage 2 will permit a within-subjects comparison of changes in CAPS-5 total score as a function of marijuana concentration, including differences in preferences for a specific marijuana concentration by self-report, and the removal of placebo as a possibility ensures that all study participants receive active marijuana at some point during the study.

Following completion of Stage 2, participants will be invited to participate in an optional Stage 3. During Stage 3, participants can choose to receive the amount equivalent to the unused and returned marijuana from Stage 1 or Stage 2 from a new supply. This design feature discourages diversion of unused marijuana and encourages participant use of marijuana in a naturalistic manner during Stages 1 and 2. Marijuana will be dispensed during Stage 3 based on the average daily rate of use during Stages 1 and 2 and will not last more than two months.

There will be a long-term follow-up assessment conducted six months after the end of Stage 2. Participants will complete the long-term follow-up questionnaire concerning their mental health, substance use, and changes in PTSD therapies and medications. A blinded Independent Rater (IR) will administer the CAPS-5. Participants will complete self-report measures and one week of Actigraphy (ACT) monitoring, followed by study termination.

4.1 Planned Duration of Study

Study duration for each participant will be eight and a half months from the time the participant is enrolled in the study. The study will start after marijuana is obtained from the NIDA Drug Supply Program, and composition may be verified by an appropriately qualified laboratory. Assuming that eight participants can be enrolled each month across sites, the study should take approximately two years to complete.

4.2 Randomization and Participant Numbering

To achieve sufficient statistical power and account for dropouts, about 116 participants will be stratified by site and randomized in a 1:1:1:1 ratio across the four treatment groups (High THC, High CBD, THC/CBD, or Placebo) based on a sequential order of enrollment into the study. Participants will be assigned a randomization code that will correspond to a blinded condition assignment. Randomization and enrollment will halt when 76 participants complete Stage 1 (at least N=19 per group). In order to maintain the blind for participants, site staff, IRs, and sponsor staff, a central electronic database will be utilized for randomization based on validated computer-generated lists. The Stage 1 randomization list will utilize blocks to balance treatment assignments. Stage 2 randomization will utilize multiple validated randomization lists that re-randomize participants in a blinded manner to one of two new treatment assignments in a 1:1 ratio, excluding the previously assigned Stage 1 dose and the placebo condition as possibilities.

The blind may be broken for an individual participant if there is an AE or other emergency requiring knowledge of the participant's marijuana condition assignment. This emergency unblinding would require approval from the site CI and Coordinating Investigator. For this purpose, the Randomization Monitor will provide dose assignment through the electronic randomization system. In all other cases, the blind will be maintained until all participants have completed the study and the database is locked. The Coordinating Investigator, Co-investigator, CIs, IR, and participant will be blind to condition assignment.

Prior to enrollment, participants at Site 01 will be tracked with a screening number assigned sequentially starting at "S1001," and participants at Site 02 will be tracked with a screening number assigned sequentially starting at "S2001." Participants who meet eligibility criteria will be enrolled in the study and assigned a five-digit participant number. The first two digits will be "01 or 02" and will identify the study site. The next three digits identify the participant within the site and will be assigned sequentially, with 101 corresponding to the first participant enrolled, e.g. the first participant enrolled at site 01 will be 01101, second 01102, and the first participant enrolled at Site 02 will be 02101, second 02102, etc.

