5.3 Removal of Enrolled Participants from the Study

Participants can withdraw consent at any time without prejudice. The CI can withdraw a participant if, in his or her clinical judgment, it is in the best interest of the participant or if the participant cannot comply with the experimental procedures and related visits that are critical for safety, and this will be recorded in the participant's source records and CRF. Participants who are not able to comply with required periods of abstinence from marijuana use will be withdrawn from treatment. If the CI withdraws a participant from treatment, the CI will explain the reason for withdrawing to the participant, and refer them to standard clinical care for PTSD. Participants who are withdrawn will not be denied care within or outside of the VA or participating institutions. Participants will be clinically monitored after withdrawal by the CI. Whenever possible, the tests and evaluations listed for the termination and outcome visits will be carried out. Efforts will be made to obtain information about AE resolutions, if applicable. All participants who sign informed consent, meet study eligibility criteria including 2 weeks abstinence period prior to randomization, and who receive initial dose of study medication will be included in intent to treat analyses (including data/outcome data for study participants who withdraw consent up to the time consent is withdrawn).

Participants who discontinue treatment during the study will not be replaced. Recruitment and enrollment will continue until 76 participants have completed the Primary Endpoint.

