6.2.1 Doses

Study participants will be assigned to receive one of four marijuana conditions based on cannabinoid content: ~12.40% THC/~0.03% CBD (*High THC*), ~0.53% THC/~13.94% CBD (*High CBD*), ~7-9% THC/~7-9% CBD (*THC/CBD*) or ~0% THC/~0% CBD (*placebo*). Marijuana will be self-administered by the participant through smoking the study material.

Participants will be introduced to the marijuana concentration and the self-administration method to be used during introductory sessions during which they will smoke the study material. The CI or qualified designee, under the direction of a Schedule 1 license holder, will supply participants with packages containing seven doses of 1.8 mg per day for self-administration daily during a three-week period. Any daily unused portions will be placed in the packaging for that day and labeled with the date of use, with all unused material returned to the CI or designee during each weekly evaluation during the period of self-administration, and at the conclusion of the three-week period of active dosing, for precise weighing. The CI or designee will store each participant’s unused study drug in a DEA approved secured container until destruction.

Table 4: Participant Distribution by Concentration and Stage

| Stage 1: N= 76 (up to 116) Participants Randomized 1:1:1:1 to the Following Four Dose Groups | | | | |
|--|----------|----------|---------|---------|
| Stage 1 Arms | High THC | High CBD | THC/CBD | Placebo |

| Stage 2: Participants from Stage 1 are Re-randomized 1:1 to the Following Dose Groups | | | | |
|---|----------|----------|---------|--|
| Stage 1 Arms | Stage 2 | | | |
| High THC | | High CBD | THC/CBD | |
| High CBD | High THC | | THC/CBD | |
| THC/CBD | High THC | High CBD | | |
| Placebo | High THC | High CBD | | |

Table 5: Marijuana Doses in Stage 1

| Dose | Min number of Participants receiving dose |
|-------------------|---|
| High THC/Low CBD | 19 |
| Low THC/High CBD | 19 |
| High THC/High CBD | 19 |
| Low THC/Low CBD | 19 |

Table 6: Marijuana Doses in Stage 2

| Dose | Approximate number of Participants receiving dose* |
|-------------------|--|
| High THC/Low CBD | 25 |
| Low THC/High CBD | 25 |
| High THC/High CBD | 26 |

* Due to enrollment and dropouts to achieve N=76 for primary endpoint, the actual number of Stage 2 participants may be higher or lower

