12.1 Statistical Power

The proposed study is a pilot investigation intended to gather preliminary data on the safety and efficacy of marijuana in people with chronic, treatment-resistant PTSD. Because of their exploratory nature, pilot studies are often not powered for detecting the desired effect. Because it is a pilot study in a small sample, results will be used to assess variability of the outcome measures as inputs for calculation of sample sizes for adequately powered subsequent studies. This study will be the first to examine the effects of marijuana on PTSD.

This pilot RCT is the first study of its kind intended to gather estimates of effect size of marijuana for PTSD. In the absence of published effect sizes of marijuana for PTSD, possible effect sizes are estimated to be 0.4 (small to medium effect) for a between-subject comparison to ensure an adequately powered study size, based on a recent meta-analysis conducted with the National Center for PTSD [172]. Thus in the proposed study, $N=76$ with 19 participants randomized to each group will have 82% power to detect these or greater differences between groups on the same primary outcome measure (change in CAPS-5 total score) used to obtain FDA approval for PTSD medications. Similar calculations would apply for secondary analyses.

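### Section 4.2 promises at least 19 Stage 1 completers in every group, but a halt at 76 completers in total does not secure that number

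*Protocol*

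**What the plan says.** - **Section 4.2, halt rule:** "Randomization and enrollment will halt when 76 participants complete Stage 1 (at least N=19 per group".
- **Section 4.2, allocation:** "about 116 participants will be stratified by site and randomized in a 1:1:1:1 ratio across the four treatment groups", which is about 29 per group. On balance it adds: "The Stage 1 randomization list will utilize blocks to balance treatment assignments".
- **Section 5.3:** "Recruitment and enrollment will continue until 76 participants have completed the Primary Endpoint". No per-group condition is given here. The sentence before it reads "Participants who discontinue treatment during the study will not be replaced".
- **Section 6.2.1:** Table 4 gives 76 participants with an upper figure of 116. Table 5 lists 19 for each Stage 1 group under the column "Min number of Participants receiving dose".
- **Section 12.1:** "with 19 participants randomized to each group will have 82% power", at an effect size of 0.4.
- **Section 12.0:** the intent-to-treat analysis takes all available outcome data from everyone randomized, including those who withdraw from treatment.

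**The concern.** The total and the per-group minimum leave no slack between them, because 4 × 19 = 76. If one group has 20 completers when the 76th is counted, another must have 18 or fewer. Blocked assignment evens out the numbers randomized, but completion depends on dropout, and the protocol describes no step that brings a lagging group up to 19.

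Sections 4.2 and 5.3 can therefore be followed faithfully to different stopping points: one at 76 completers, the other when the slowest group reaches 19. The first does not secure the stated minimum. The second normally exceeds the stated total, and at the implied dropout it usually exceeds the stated number randomized. A halt rule should not leave that choice to be made during the trial, least of all by anyone who can see completer counts by group.

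**Working it through.** **Inputs from the protocol.** 76 completers, 19 per group, about 116 randomized 1:1:1:1 and stratified by site (4.2); eight enrolled per month across sites (4.1); effect size 0.4 and 82% power (12.1); alpha 0.05 (12.0).

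**Assumptions.** No dropout rate is stated. The pair 76/116 implies 65.5% retention (34.5% dropout), and lower dropout is shown as a range. Block size (4 or 8), two equal sites, about 24 days from enrolment to the Stage 1 endpoint, and independent dropout at the same rate in every group are also assumed.

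**1. The plan's power figure.** For an overall four-group F test with Cohen's f = 0.4 and N = 76, the noncentrality is 0.4² × 76 = 12.16, the degrees of freedom are 3 and 72, and the critical value is 2.73. Power is 82.3%, so the stated 82% reproduces when 0.4 is read as f.

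**2. Counting stops at the 76th completer.** With 29 per group and 76 completers falling at random among 116:

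P(19 in every group) = C(29,19)⁴ / C(116,76) = 0.0073, or 0.7%.

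Simulation with blocked assignment and enrolment stopped at the 76th completer:

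| Dropout | P(every group ≥ 19) |
|---|---|
| 34.5% | 0.6–0.8% |
| 25% | 1.2% |
| 20% | 1.6–1.8% |
| 10% | 3–4% |
| 5% | 6.5–9.5% |

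At 34.5% dropout the smallest group averages 16.3 completers (5th to 95th percentile 14 to 18).

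**3. Participants already in Stage 1 are followed to the endpoint.** At eight per month, about 8/30.4 × 24 = 6.3 participants are in Stage 1 when the 76th completes. At 65.5% retention they add about 4.1 completers, giving about 80 in all.

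| Dropout | P(every group ≥ 19) | Mean total completers |
|---|---|---|
| 34.5% | 20% | 80 |
| 20% | 40% | 81 |
| 10% | 64% | 82 |
| 5% | 82% | 82 |

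**4. The bracket is a second halt condition.** Enrolment then runs until every group has 19 completers. Expected completers are the mean number randomized times retention.

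| Dropout | Mean randomized | Expected completers | 116 is enough |
|---|---|---|---|
| 34.5% | 131 (95th percentile about 154) | 131 × 0.655 = 86 | 11–12% |
| 20% | 104 | 104 × 0.80 = 83 | about 92% |
| 10% | 90 | 90 × 0.90 = 81 | all runs |

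Direct check of the last figure in the first row: with 29 per group and 65.5% retention, P(at least 19 complete) is 0.585 per group, and 0.585⁴ = 0.117.

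**5. Effect on power.** With completers only, f = 0.4, the stop of step 2 and 34.5% dropout, average power of the overall F test is about 82%. The 5th percentile is 75% if a single group differs from the other three and 82% for a two-against-two pattern. With the follow-up of step 3, average power is about 84%.

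**The case against.** The strongest reply has four parts.

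1. **The halt applies to randomization and enrolment, not to follow-up.** Participants already in Stage 1 go on to the endpoint, so the even-split probabilities in step 2 are too harsh as a forecast of final group sizes. This stands. A reader might infer that 19 per group is almost never reached; that is true only of the count at the 76th completer. The minimum is still missed in about 80% of trials at the implied dropout and 36% at 10% dropout, so it is not a guarantee.
2. **The bracket may be a joint condition.** The text permits this, and the central randomization system could apply it without unblinding the sites. The minimum is then met by definition. But the total normally passes 76, which 5.3 does not provide for, and at the implied dropout 116 randomized usually falls short.
3. **Power is not undermined.** A reader might infer that the 82% fails. The document does not support that: 12.1 speaks of 19 randomized per group, about 29 per group are to be randomized, the intent-to-treat set is not limited to completers, and chance imbalance hardly moves average power. A small placebo group would weaken active-versus-placebo contrasts, but the 82% does not describe those.
4. **Table 5 and the replacement sentence are sound.** Table 5 counts participants receiving the dose, and about 29 randomized per group should meet 19 easily. Not replacing a dropout is compatible with enrolling until a total is reached. Both points stand.

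The trial also calls itself a pilot, which lowers the stakes but does not make the halt rule clear.

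**Conclusion.** The point holds as a stated group size that the halt rule does not secure. At the 76th completer, at least 19 in every group requires exactly 19/19/19/19. That has a probability of 0.7% at the implied 65.5% retention and about 1% to 4% at 75% to 90%. Following participants already in Stage 1 raises it to about 20% at 34.5% dropout and 64% at 10%. Reading the bracket as a joint condition meets the minimum but breaks the total in 5.3 and, at the implied dropout, usually the figure of 116.

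That the total and the minimum leave no slack is arithmetic from the protocol and needs no assumption. The probabilities rest on the assumed retention, block size, site split and transit time, and on equal dropout across groups; unequal dropout would lower them. Average power of the overall test is barely affected. Section 12.1 does leave one ambiguity: it attaches 19 per group to participants randomized, while 4.2 attaches the same number to completers.

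**What to change.** State one halt rule and use it in both 4.2 and 5.3. The simpler choice is a halt at 76 Stage 1 completers in total, about 19 per group on average, with the words at least removed from 4.2. Say also whether participants already in Stage 1 at the halt continue to the endpoint and are counted. In 12.1, state whether 19 per group means randomized or completing.

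If a true per-group minimum is wanted, write it as the halt condition in both sections, have the central randomization system apply it, and set a cap on the number randomized. At the implied dropout the cap would have to allow for about 131 on average and about 154 at the 95th percentile, rather than 116.

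Table 5 and the sentence on replacement can stay. No expected size for the smallest group should be written in, since it would rest on a retention rate that the protocol does not state.

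The preferred version costs wording and a slightly less favourable stated group size, with no extra participants. The per-group version costs about 15 more randomized on average at the implied dropout (131 − 116).

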2.3 Rationale for Concentration Selection

Four potencies of marijuana obtained through the National Institute on Drug Abuse (NIDA) drug supply program that vary in THC and cannabidiol CBD content will be used: High THC/ Low CBD (*High THC*), Low THC/High CBD (*High CBD*), High THC/High CBD (*THC/CBD*) or Low THC/Low CBD (*placebo*) marijuana. “High” is defined as marijuana containing a target of 9-15% concentration by weight of the respective cannabinoid and “Low” is defined as <2% concentration by weight; actual cannabinoid concentrations are subject to the capabilities of the NIDA Drug Supply Program to produce different strains of marijuana based on these targets and are provided in Section 6. In the Stage 2 crossover, two of three concentrations will be compared: High THC, High CBD, and THC/CBD. *Ad-libitum* self-administration will be permitted up to a maximum of 1.8 grams of marijuana/day.

The doses of marijuana (excluding placebo) in this study were chosen because they contain a range of THC and CBD ratios and potencies generalizable to what many veterans are currently using to manage PTSD symptoms in non-clinical settings in states with legalized medical marijuana. Prior to the study start, laboratory testing of the study marijuana will be completed to verify the chemical composition of each concentration group.

The active (non-placebo) doses are expected to produce commonly reported subjective effects of marijuana. The physiological effects are expected to be tolerable based on previous observational studies in the literature. The placebo is expected to produce

minimal side effects, without the full range of psychological and subjective effects seen with the active doses.

Analysis of the differential efficacy of these distinct marijuana concentrations will help elucidate whether the ratio of THC to CBD is a significant factor in the attenuation of PTSD symptoms, as reported anecdotally and based on the differential pharmacology of THC and CBD. *Ad-libitum* use will provide the most naturalistic comparison to real world examples of smoked marijuana.

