3.2 Secondary Objectives

The following secondary objectives will be used to support the results of the primary objective:

1. Assess independent effects of three active concentrations of marijuana and placebo in reducing self-reported symptoms of PTSD with the PCL-5, anxiety and depression with the IDAS, and improving psychosocial functioning with the IPF and WBR (self-report and observer) among veterans during Stage 1.
2. Assess independent effects of three active concentrations of marijuana and placebo in reducing self-reported symptoms of PTSD with PCL-5, anxiety and depression with IDAS, and improving psychosocial functioning with the IPF and WBR (self-report and observer) among veterans during Stage 2.
3. Assess comparative efficacy between placebo and each active dose of marijuana based on a within-subjects analysis of PTSD symptoms as measured by the CAPS-5 in crossover participants at Baseline, End of Stage 1, Stage 2 Baseline, and End of Stage 2.
4. Assess whether Stage 2 crossover participants' preferences for marijuana concentrations in Stage 1 and Stage 2 correlate with reduction in PTSD symptoms as measured by the CAPS-5 total score.
5. Assess whether participants experience a clinically significant increase in PTSD symptoms based on CAPS-5 and PCL-5 total scores during the washout period between Stage 1 and Stage 2 compared with measures assessed at Baseline and during Stage 1.
6. Explore correlation of treatment outcomes measured by CAPS-5 score with objective changes in sleep via Actigraphy throughout the study and self-reported

- changes in sleep quality using the ISI on a weekly basis.
7. Explore correlation of Daily Diary items related to sleep with objective changes in sleep via Actigraphy and self-reported changes in sleep quality using the ISI on a weekly basis.
 8. Explore correlation of treatment effects measured by CAPS-5 total score with amount of marijuana used based on Daily Diary across Stage 1 and Stage 2.
 9. Explore treatment outcomes measured by CAPS-5 total score by marijuana concentration, with concomitant substance and medication use as a covariate throughout the treatment period.
 10. Explore durability of treatment outcomes measured by CAPS-5 total score, with any PTSD treatments based on the LTFU questionnaire treated as a covariate, six months after completing Stage 2.

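### The Stage 2 group sizes in Table 6 (25/25/26) cannot come from the two-option 1:1 re-randomization in section 4.2 and Table 4, which gives about 28.5/28.5/19

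*Protocol*

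**What the plan says.** All references are to the protocol.

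- **Section 4.2** assigns each participant in Stage 2 to "one of two new treatment assignments in a 1:1 ratio, excluding the previously assigned Stage 1 dose and the placebo condition as possibilities".
- **Section 6.2.1, Table 4** repeats the ratio in its heading: "Participants from Stage 1 are Re-randomized 1:1 to the Following Dose Groups". Each of its four rows lists two options. The placebo row reads "Placebo | High THC | High CBD", with the THC/CBD cell empty.
- **Section 6.2.1, Table 5** gives a minimum of 19 participants for each of the four Stage 1 types, including "Low THC/Low CBD | 19" for placebo. The total is 76.
- **Section 6.2.1, Table 6** gives approximate Stage 2 sizes of 25 for High THC, 25 for High CBD and "High THC/High CBD | 26" for THC/CBD. The total is again 76. Its footnote says that, because of enrollment and dropouts, "the actual number of Stage 2 participants may be higher or lower".
- **Section 2.3** says of the crossover: "In the Stage 2 crossover, two of three concentrations will be compared".
- **Section 4.0** removes placebo from Stage 2 and requires a type other than the one received in Stage 1. It does not limit the choice to two.
- **Section 3.2, Secondary Objective 3** is to "Assess comparative efficacy between placebo and each active dose of marijuana based on a within-subjects analysis of PTSD symptoms" in crossover participants, using CAPS-5 at four assessments.

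**The concern.** The allocation rule and the group sizes describe two different randomization schemes. Under the rule THC/CBD is the smallest Stage 2 group; in Table 6 it is the largest.

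Section 4.2 is also inconsistent within itself for the placebo arm. Its two exclusions, the participant's own Stage 1 dose and placebo, are the same thing for someone who had placebo. Three active types therefore remain, not two. Section 4.0 leaves the same three.

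The choice of scheme settles three things:

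- how many participants receive each type in Stage 2;
- whether any participant contributes a direct placebo versus THC/CBD comparison to Secondary Objective 3;
- whether the Stage 2 groups are balanced on prior placebo exposure. Section 5.2.5 notes that participants who had placebo receive active marijuana for the first time in Stage 2.

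**Working it through.** **Inputs.** Let a, b, c and d be the numbers entering Stage 2 from the High THC, High CBD, THC/CBD and placebo arms. Take a = b = c = d = 19 (Table 5; Tables 5 and 6 both sum to 76).

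**Step 1: the rule in section 4.2 and Table 4.**

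- High THC = (b + c + d)/2 = 57/2 = 28.5
- High CBD = (a + c + d)/2 = 57/2 = 28.5
- THC/CBD = (a + b)/2 = 38/2 = 19

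**Step 2: look for a scheme that gives Table 6.** If the placebo arm is split equally over all three active types, each type receives 19 from the other active arms plus 19/3 = 6.33. That is 25.33 each, which rounds to 25/25/26.

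| | High THC | High CBD | THC/CBD |
|---|---|---|---|
| Table 4 at 1:1 | 28.5 (37.5%) | 28.5 (37.5%) | 19 (25%) |
| Table 6 as printed | 25 (32.9%) | 25 (32.9%) | 26 (34.2%) |
| Three-way placebo split | 25.3 | 25.3 | 25.3 |

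**Step 3: does the mismatch depend on the empty cell in Table 4?** No. If the placebo arm is split 1:1 over any fixed pair of active types, two types reach 19 + 9.5 = 28.5 and the third stays at 19. No pair gives 25/25/26.

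**Step 4: could unequal Stage 1 arms explain it?** Setting the Step 1 formulas equal to 25, 25 and 26 gives b + c + d = 50, a + c + d = 50 and a + b = 52. The only solution is a = b = 26 and c + d = 24, against 19, 19 and 38 in Table 5. If every arm entering Stage 2 lies between 19 and 29 (116/4), the THC/CBD share is largest at a = b = 29 and c = d = 19. That gives 33.5/33.5/29, and 29/96 = 30.2%, still below 34.2%.

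**Step 5: could a change in total explain it?** With 29 per arm entering (116 in all) the rule gives 43.5/43.5/29. THC/CBD stays at 25%, so dropout that is equal across arms does not even out the groups.

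**Step 6: chance.** Under unblocked 1:1 lists, the number going to THC/CBD is Binomial(38, 0.5), and P(26 or more) = 0.017.

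**Step 7: consequences.**

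| | Table 4 (High THC / High CBD / THC/CBD) | Three-way split |
|---|---|---|
| Expected direct pairs with placebo | 9.5 / 9.5 / 0 | 6.3 each |
| Share of Stage 2 group coming from placebo | 9.5/28.5 = 33% / 33% / 0% | 6.33/25.33 = 25% each |

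**The case against.** The arithmetic mismatch is not in dispute. The case for giving it little weight has five parts.

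- **The empty cell.** That nobody receives both placebo and THC/CBD rests on one blank cell in Table 4, which could be damaged in the text read from the PDF and should be checked there. This stands as a condition on the points about Objective 3 and prior placebo exposure. The conflict over group sizes does not need the cell (Step 3).
- **Section 2.3.** Its wording gives no ratio and may only describe which types a participant compares. It is weak support, and the finding does not depend on it.
- **Supporting figures.** The 30.2% is not an absolute ceiling, because 19 is the minimum completing Stage 1, not the minimum entering Stage 2. With 29, 29, 13 and 13 entering, Table 4 gives 27.5/27.5/29, a THC/CBD share of 34.5%. That needs strongly differential dropout, which is no basis for a planning table. The binomial probability is also secondary, since Table 6 is a plan and not an observed allocation.
- **Limited consequence.** Objective 3 uses four CAPS-5 assessments, and a model using all of them can still estimate the THC/CBD versus placebo contrast. Even a three-way split yields only about six direct pairs per type. Section 12.0 runs the Stage 2 analysis only if Stage 1 shows an effect, with Stage 1 data as a covariate. All this is fair and limits the weight of the point.
- **A stale table.** Assignment is by validated lists, Table 6 is headed as approximate, and section 4.2 and Table 4 agree, so Table 6 may simply be out of date. It may be, but section 4.2's own exclusions and section 4.0 leave three types for the placebo arm, as Table 6 implies. The document does not settle which scheme is meant.

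**Conclusion.** The concern holds. Section 4.2 and Table 4 give 28.5/28.5/19, and Table 6 states 25/25/26. The differences are 3.5, 3.5 and 7 participants, and the rank of THC/CBD is reversed. Among the schemes tried, only an equal three-way split of the placebo arm reproduces Table 6.

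The figures assume that 19 per Stage 1 arm enter Stage 2. The conclusion also holds for any arm sizes from 19 to 29 and for any fixed pair of types for the placebo arm. The statements that there are no direct placebo versus THC/CBD pairs, and that no participant in the Stage 2 THC/CBD group comes from placebo, hold under Table 4 as printed.

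The effect is confined to Stage 2 and the secondary objectives; the primary Stage 1 comparison is untouched. It should be fixed, because lists built from Table 4 and lists built to meet Table 6 would be different lists, and allocation cannot be corrected once made.

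**What to change.** Reconcile section 4.2, Table 4 and Table 6 to one scheme before the Stage 2 lists are used. Which scheme is intended is for the sponsor to state.

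- **If the placebo arm is to be split over all three active types:** add THC/CBD to the placebo row of Table 4, and correct the two-option 1:1 wording for that arm in section 4.2 and in the Table 4 heading. Build the Stage 2 list for the placebo arm to match. Table 6 then stands.
- **If Table 4 is intended:** change Table 6 to about 28–29, 28–29 and 19. Name in section 4.2 the two types open to the placebo arm, since the stated exclusions leave three. State in Secondary Objective 3 that the THC/CBD versus placebo comparison has no direct within-person pairs.

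The cost is a few table cells and sentences and, in the first case, one randomization list. No extra participants or visits are needed.
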